## SUMMARY

Atherosclerosis is the leading cause of morbidity and mortality in Type II diabetes. A cell type called the monocyte/macrophage is critical to development and complications of atherosclerosis. This project will evaluate the effectiveness of a medication called Spironolactone in preventing atherosclerosis in Type II diabetes through its effects on cells such as the monocyte. Spironolactone has been demonstrated to be effective for the treatment of patients after a heart attack and stroke. We will evaluate the impact of Spironolactone in reducing atherosclerosis plaque and additionally evaluate its potential in changing inflammation. We envision that our strategy of simultaneously probing effect of a drug combined with analysis of mechanisms of action and predictive response will likely provide key information with which to design hard event (heart attack, stroke etc.) based trials.

## BACKGROUND

Pharmacological studies over > 20 years have defined the importance of the mineralocorticoid receptor (MR) in hypertension and heart failure. Large-scale clinical trials have validated the use of MR antagonists in the management of patients with heart failure (RALES, EMPHASIS) and post myocardial infarction (EPHESUS)1-4 . Recent studies suggest that MR may link metabolic dysregulation with susceptibility to type II diabetes (T2DM) and atherosclerosis5-12 . MR is an ancient member of the 51-member, steroid-thyroid-retinoid receptor family. In response to ligand binding, MR undergoes conformational changes and is translocated to the nucleus where it binds to response elements in promoters, increasing transcription of target genes 13,14 . Although effects of MR activation have been attributed to aldosterone, mechanisms independent of aldosterone have been suggested and play a role in promoting inflammation, fibrosis and target organ damage15-18 .

**Cardiovascular Effects of MR Activation:** MR is widely expressed in the cardiovascular system 19-22 and is a major determinant of endothelial function, smooth muscle tone, vascular remodeling, fibrosis and blood pressure (BP)23-36 . In vitro, animal, and human data support a role for MR activation in promoting vascular oxidative stress, inflammation, proliferation, migration, vasoconstriction, vascular remodeling and fibrosis (FIG. 2) 5,28,31,36-44 . Similarly, MR antagonism is anti-inflammatory and antifibrotic with evidence in humans indicating reversal of endothelial dysfunction, diastolic dysfunction and vascular stiffness45-49 .

[figure not shown]
**FIGURE 2.** Adverse consequences of MR activation.

**MR Activation Links Insulin Resistance (IR), Inflammation and Atherosclerosis:** A number of reviews have already detailed in-vitro, experimental and human evidence linking aldosterone/MR activation with IR but is briefly summarized here. The visceral adipose renin-angiotensin-aldosterone (RAS) system synthesizes aldosterone, expresses MR, and predicts IR in both humans and animal models. MR expression on macrophages could potentially play a pro-inflammatory role in tissues such as adipose and vasculature. MR blockade/deletion has been shown in both experimental and human studies to ameliorate IR. MR activation may affect IR through multiple mechanisms that include attenuation of insulin signaling in the heart, vasculature, and skeletal muscle. This may include impairment of expression of insulin receptor and substrate, decreased GLUT4 expression, abnormal phosphorylation of IRS, and activation of multiple stress kinases downstream of insulin receptor/IRS (leading to attenuation of insulin signaling). MR activation also promotes hepatic oxidative stress, gluconeogenesis and enhances hyperglycemia. Recently, MR activation has been shown to promote lipid storage in brown adipose and inhibit UCP1 expression. Consistent with these roles, MR antagonism in humans improves IR. Relevant to this proposal we have provided evidence for a role for MR in pro-inflammatory macrophage phenotype and reduction in atherosclerosis in animal models.

**Role for the MR in Inflammation:** Studies by [name] (co-investigator) and Chawla have provided the conceptual framework for understanding macrophage polarization state in the context of insulin resistance, obesity, and atherosclerosis. Macrophages display heterogeneity of function depending on their micro-environment. Th1 signals such as LPS/IFN $\gamma$  result in “classical activation” leading to iNOS mediated NO production and synthesis of TNF- $\alpha$  and IL-6. In contrast, an alternatively activated (A $\Phi$ ) state of macrophage is generated upon exposure to IL-4/IL-13, which are generally implicated in resolution of inflammation and tissue repair. Analysis of markers of A $\Phi$  have provided a remarkably conserved and stereotypic signature of genes corroborated by recent

genome-wide analysis of macrophage function. Although AΦ has been implicated in a range of physiologic and pathological processes, including inflammation, repair, and metabolic function, its role in atherosclerosis continues to evolve. PPAR $\gamma$  activation of macrophages by glitazones both *in vitro* and *in vivo* in patients with atherosclerosis, induces AΦ while deletion or antagonism (in mice) contributes to a classically activated phenotype. In contrast to the function of PPAR $\gamma$ , MR activation potentiates classical activation while deletion of MR or antagonism results in AΦ. The relative contribution and relevance of AΦ in atherosclerosis is not well studied. Studies in humans that provide insights on the role of AΦ and factors that may modulate macrophage phenotype may provide novel insights in atherosclerosis. Recently microRNAs (miRNAs) via their role as regulators of gene networks may represent mediators of functional networks and phenotypes such as AΦ and may provide insights into risk in atherosclerosis. We have provided important links between candidate miRs that play a role in macrophage AΦ through MR. We propose studies to investigate this in a clinical trial of MR antagonism in patients with T2DM.

**Rationale for miRNA's as Regulator of AΦ and Marker(s) of Risk/Response:** miRNAs hold the potential to modulate complex physiological/disease phenotypes and/or response to therapies by regulating entire functional networks. miRNAs are non-coding RNAs of 18–25 nucleotides that regulate multigene expression and modulate entire biologic pathways. It has been estimated that up to 1000 miRNAs are encoded by the human genome. miRNAs are transcribed as precursors called primary miRNAs, which are processed to form mature miRNAs. Mature miRNAs recognize specific target mRNAs and induce gene silencing by mRNA degradation and/or inhibition of translation. Assessment of miRNAs may provide insights into mechanisms of action/effect of therapies. In support of this, miRNAs are risk predictors in cancer and emerging studies suggest that miRNAs may predict risk in cardiovascular disease.

**FIGURE 3.** miRs and transcription factors such as MR regulate entire functional gene networks that through an intermediate phenotype (alternate macrophage activation) may affect atherosclerosis.

### Preliminary Studies

**MR antagonism is associated with Improvements in Vascular Function and Plaque Burden:** Proof-ofconcept experiments from our group using two different MR antagonists (Eplerenone and

Spironolactone) in two distinct models of atherosclerosis provide experimental/mechanistic basis for the proposed investigation. In the first model, New Zealand white male rabbits were fed 1% cholesterol chow (HL) or normal chow (NC) over 8 weeks to induce atherosclerosis and then randomized to receive Eplerenone or placebo (Epl10 mg/kg) for 6 additional weeks. Eplerenone normalized peak endothelium dependent relaxation while nitroglycerin responses were unaltered (data for nitroglycerin not shown) (FIG. 4). Since we and others have established the importance of NADPH derived superoxide inactivation of •NO in response to angiotensin II (AII) and aldosterone, we investigated these sources 94-98 . Treatment with Eplerenone reduced •O2 - in aorta. We then studied the effects of Eplerenone in high-fat fed LDLR-/- model (Eplerenone 10 mg/kg for 12 weeks). Similar improvements in endothelial dilation in the LDLR-/- were seen (FIG 4). Epl reduced atherosclerosis and macrophage infiltration. These same data have been reproduced in the ApoE-/- by other groups 99,100 . In additional experiments, we have demonstrated that Eplerenone treatment prevents aldosterone induced thrombosis101 .

**Role of the MR in Control of Macrophage Polarization:** In collaboration with [name], we and others have shown that various pro-inflammatory insults including highfat feeding and air-pollution can result in a shift to an M1 phenotype 72,102-104 . Cytokines from an M1 polarized macrophage, such as TNF $\alpha$  and CCL-2 play an important role in potentiation of inflammation and insulin resistance. Usher and [name] et al have recently shown that peritoneal macrophages in mice could be rendered pro-inflammatory via exposure to aldosterone, an effect prevented by Eplerenone but not the GR antagonist RU486 85 . Deletion of MR in myeloid cells recapitulated the effects of MR antagonism, by shifting phenotype to an alternately activated form concomitantly down regulating proinflammatory and profibrotic genes (TGF $\beta$  and PAI-1). IL-4, an inducer of A $\phi$ , synergized with macrophages lacking MR to display enhanced expression of A $\phi$  markers. In vivo the effects of myeloid deletion of MR reduced, aortic and cardiac macrophage recruitment, cardiac hypertrophy, fibrosis and fetal gene re-programming in response to AII and L-NAME (model of MR activation) suggesting that myeloid MR was crucial to adverse cardiovascular remodeling 85 . Finally gene expression analysis revealed significant similarity between MR deletion and PPAR $\gamma$  activation.

**Bioinformatic and in vitro assessment of miRNA regulation of NR3C2 (MR gene) in human monocytes:** We first asked if NR3C2 is a target for miRNA regulation and investigated this using in-silico approaches. NR3C2 has one of the longest 3'-UTR's in the RAS cascade and contains the highest number of predicted miRNA targets based on Targetscan 5.2 analysis indicating that it may be under intricate miRNA control.

Fifteen miRNAs including 2 unique miRNA families (miR-30 and miR129) were identified that bound to 11 distinct sites on the 3'-UTR. These miRNAs were then analyzed in 10 miRNA prediction algorithms (Diana, MicroInspector, Miranda, mirtarget2, mitarget, nbmirtar, pictar, pita, rna22, rnahybrid). miRNAs that were common to at least 5 different prediction algorithms were identified. Based on this analysis, we investigated the expression of miRNAs initially identified in-silico, in human monocytes and then investigated their regulation in monocytes derived from a cohort of patients with atherosclerosis (derivation cohort, n=10; mean age=65±6 years) using an expression array with >600 miRNAs (Nanostring Technologies. All patients in the derivation cohort were receiving ACEI/ARB/statin therapy and were compared to control subjects without risk factors for atherosclerosis (n=6 per group). We used a miRNA expression array (Nanostring Technologies, CA) that provides quantitative assessment of >600 human miRs. miR's regulated in atherosclerosis were defined as those that were highly regulated (p<10-10 vs. control subjects). The data set was filtered for outliers and analyzed. The putative miRNAs that target NR3C2, are expressed in monocytes AND are downregulated in atherosclerosis. We then analyzed

the relationship of miRNAs obtained in the derivation cohort, with aortic plaque measured by MRI. Correlation analysis with baseline atherosclerosis revealed that multiple miRs correlated with atherosclerosis plaque burden at baseline after adjustment of baseline covariates (age, gender, blood pressure and LDL cholesterol). This included 31 miRNAs involved in NR3C2 regulation ( $r^2 = 0.35$ ) as well as several candidate miRs unrelated to MR expression (Down-regulated=miR-27,  $r^2 = 0.36$ ; miR-125,  $r^2 = 0.25$ ; miR-124,  $r^2 = 0.20$ ; miR-7  $r^2 = 0.19$ ; Up-regulated: miR-223.  $r^2 = 0.25$ ; mir-126.  $r^2 = 0.22$ ; miR-1720,  $r^2 = 0.15$ ).

**Regulation of NR3C2-3UTR Luciferase Reporter:** NR3C2 3-UTR was cloned downstream of a mammalian promoter-luciferase system and co-transfected in HeLa cells with plasmids expressing pmiR-19b and pmiR-124 have shown that 124 but not 19b reduced luciferase activity by more than 50%. Studies examining other miRNAs in HeLa cells are currently ongoing in the laboratory.

**Assessment of Aortic Atherosclerosis at 3.0T MR using SPACE:** We have described the implementation of a modified spin echo sequence T1W-SPACE and have successfully implemented this technique at both 1.5T and 3.0T. We have developed a customized tool-set for assessment of plaque area over the aorta.

**Plaque Progression over 9 months:** In a recently concluded study in patients with established vascular disease on complete renin blockade with Aliskiren (ALPINE, n=37). The results of this study demonstrated that aliskerin use on top of ACEI/ARB progresses atherosclerosis. These results are consistent with results of ALTITUDE published recently. Interestingly one of the findings in the study was that aliskerin treatment resulted in decrease of miR-19a which we have shown to be important in upregulation of MR. This increase was particularly robust in those on ACEI/ARB therapy suggesting that this group could be potentially sensitive to the effects of MR blockade as they are overexpressing MR (product of NR3C2 gene).

## **STUDY RATIONALE**

There are multiple innovative concepts in this trial. 1) There are currently no large trials of MR antagonism in patients with diabetic atherosclerosis and no trials that are investigating predictors of response. Our results will provide a basis for a definitive intervention trial. 2) Investigation of monocyte/macrophage polarization: The importance of monocyte/macrophage activation states in metabolic and cardiovascular disease is yet to be fully integrated into our understanding. Our preliminary studies and those by others support an important role for MR in AΦ, but whether or not pharmacologic blockade of MR modifies monocyte inflammation in humans is unknown. 3) Investigation of miRNAs: Prior studies have shown that miRNAs are involved in monocyte differentiation and inflammatory function. Our approach to incorporate miRNA analysis to predict response is innovative and is based on preliminary data suggesting that several candidate miRNAs regulated MR expression and AΦ. 3) MRI Approaches in Aortic Imaging: MRI approaches can track serial changes in atherosclerosis. Prior MRI approaches have assessed the carotid or a limited portion of the descending thoracic aorta (a relatively immobile structure) not susceptible to motion artifacts. Current improvements in pulse sequence design have enabled motion-free high-resolution coverage of the entire aorta including the arch. We have tested the ability of such an approach for wholebody plaque, carotid and lower extremity imaging. Coverage of the entire aorta allows detection of smaller changes, allows inclusion of smaller numbers of patients and provides an

improvement over invasive surrogate measures acquired in limited portions of the arterial bed (83-86).125,126 4) Focus on monocyte miRNAs (versus plasma): While plasma miRNAs are under investigation as biomarkers, miRNA detection is limited by low amounts of RNA, lack of standardization, and lack of endogenous controls. In addition, since plasma miRNA expression is likely the result of several cell types, the biological and mechanistic relevance of changes are challenging. Peripheral blood mononuclear cells (PBMCs) provide unique advantages over plasma miRNAs in atherosclerosis (see below). Evidence of the importance of miRNAs in peripheral blood mononuclear cell (PBMC) is well established in diseases such as cancer and COPD 89,127- 130 . 5) miRNAs as Predictors of Response/Disease: Atherosclerosis is a complex disease and it is unlikely that expression of a single gene or marker may predict it. However understanding of candidate miRNAs and key factors such as MR through their role in regulating hundreds of genes and influencing phenotypes such as AΦ are far more likely to be informative. The figure illustrates this concept where miRNAs and the transcription factor MR may potentially influence functional networks of genes and thereby affect AΦ. Our investigations thus may shed light on the role of each of these “levels” of regulation in atherosclerosis.

### **Risk / Benefit Assessment**

All potential patients will be informed of the potential side effect profile prior to enrollment in the study and full informed consent will be utilized.

### **Risks of an MRI Scan**

There are no risks associated with the MRI scan. In our center approximately 10% of patients are genuinely claustrophobic.

### **Reproductive Risks**

Spironolactone may cause risks to the unborn fetus and or the baby of a nursing mother. Therefore, pregnant women and women who are nursing their babies should not participate in the study. Woman must be either post-menopausal for one year, surgically sterile, or using effective contraception. A pregnancy test will be required at screening for all woman who may become pregnant. A negative test is required for the individual to enroll in the study. Participants who become pregnant will report to the study PI immediately, and stop taking the pills.

Spironolactone can decrease the effectiveness of birth control pills. Women who use oral birth control methods will be excluded from the study. Women of child bearing potential should use another reliable form of contraception. Acceptable methods of birth control include subcutaneous implants, intrauterine devices (IUD), barrier methods, surgical sterility, transdermal birth control patch, and abstinence.

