**Figure 7. Vanguard Phase**

### Main Study Phase

The Main Study Phase is a multi-site, double-blind, randomized, placebo-controlled trial with spironolactone. 130 subjects are planned. There will be 4 phases (screening, placebo run-in, dose escalation and treatment phase (FIG. 8). All patients will be carefully evaluated for study eligibility during screening prior to randomization and will be recruited from clinics at the University Hospitals Cleveland Medical Center as well as nephrology clinics. The 2-week single-blind lead-in period will permit assessment of patient compliance as well as determination of baseline sitting blood pressures. Patients must have met all inclusion/exclusion criteria before being randomized 1:1 to Placebo or Spironolactone 12.5 mg on Week 0 (Visit 2). Patients will be escalated to 25 mg daily Spironolactone or maximal tolerated dose over a 4-week period with safety checks on K+ and creatinine (FIG. 8).

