### Inclusion Criteria

1. Male or female patients > 45 or > 40 years with known atherosclerotic events (examples include MI, Stroke) and able to provide informed consent (females must be either post-menopausal for one year, surgically sterile, or using effective contraception. Oral contraceptives are disallowed).
2. Patients with type II diabetes with HbA1c ≤ 9.0 on stable anti-glycemic regimen that may include oral and/or injectable therapy (GLP-1/Insulin etc.). Changes in dose of glycemic regimen is allowed during the course of the trial if felt to be clinically appropriate.

3. GFR <90 and evidence of proteinuria (Urine Albumin/Creatinine Ratio of >30 mg/g or equivalent) in a urine specimen within 12 months OR GFR <60 mg/g regardless of proteinuria.
4. Patients must be on ACE and/or ARB therapy with no planned dose adjustments.

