#### **Exclusion Criteria**

1. Uncontrolled hypertension (SBP>160 and/or DBP>95 mmHg at visit 0 (screening) Protocol Number: 09-16-32 Confidential Version #: 1.5 Revised 01 April 2020 Page 14 of 39 and SBP >145 mm Hg at visit 2).
2. GFR (MDRD) of <15 at visit 0 (screening)
3. Hyperkalemia defined as serum K+ $\geq$  5.1 meq/L at visit 0 (screening)
4. LDL cholesterol >150 mg/dL
5. Plasma triglycerides > 400 mg/dl
6. Contraindications to MRI (metallic implants, severe claustrophobia).
7. Acute coronary syndrome, Transient ischemic attack, CVA or critical limb ischemia during the last 6 months or coronary/peripheral revascularization within the last 3 months.
8. Evidence of a secondary form of hypertension
9. Initiation of new therapy with statins, ACEI/ARB, antioxidants, CCBs, diuretics,  $\beta$  blockers
10. Type I diabetes mellitus
11. Known contraindication, including history of allergy to Spironolactone
12. Any surgical or medical condition which might alter pharmacokinetics of drug (e.g. renal transplant, liver failure, liver transplant)
13. Concurrent potentially life threatening arrhythmia or symptomatic arrhythmia.
14. Significant hyponatremia defined as Na<130 meq/L
15. History of prior malignancy including leukemia and lymphoma (but not basal cell skin cancer, cured squamous cell cancer and cured prostate cancer).
16. History of any severe, life-threatening disease.
17. Any surgical or medical conditions which place the patient at higher risk derived from his/her participation into the study, or likely to prevent patient from complying with requirements
18. History of drug abuse within the last 2 years, noncompliance and unwillingness/inability to consent
19. Pregnant women and nursing mothers
20. Class III or IV Congestive Heart Failure
21. Primary Hyperaldosteronism

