## **STUDY TREATMENTS**

### **Method of Assigning Subjects to Treatment Groups**

After the placebo run-in phase, eligibility with regards to blood pressure will be reassessed.

Up to 130 eligible patients will be randomly assigned to Spironolactone or placebo treatment groups in a 1:1 ratio using a computer-generated randomization scheme developed by the statistician.

All study participants will undergo a two week run-in period with placebo. Then study medication will be commenced at 12.5 mg Spironolactone or placebo and escalated to 25 mg Spironolactone or placebo over 4 weeks. Then the treatment phase will commence with tolerated dose of Spironolactone or placebo for 48 weeks.

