### Main Study Phase

TABLE 4	SCREEN		RUN-IN PHASE		RANDOMIZATION PHASE										
					DOSE ESCALATE				TREATMENT PHASE						
	MONTH*	M1	M1	M2	M2	M 2	M 3	M 5	M 7	M 9	M 11	M 12	M 13		
WEEK	W 1	W2	W3	W4	W5	W6	W8	W9	W11	W17	W25	W33	W41	W45	W53
VISIT NUMBER	0		1	2	3	4	5	6	TF1	7	TF2	TF3	TF4	8	
Screening Labs (BMP, Lipid panel, HbA1C, Urine sample Alb/Creat)	X														
Safety Lab (BMP)				X	X	X	Opti onal	X		X					X
History/ Targeted assessment		X								X					X
EKG		X													
Vital Signs or 24-hour BP cuff *( includes central aortic BP)	X	X	X*		X		X*		X						X
Phone Call								X		X	X	X			
MRI				X											X
Research Labs/Monocyte Studies, including PIP, PIIINP, CITP and chemokines CCL2, CX3, CL1, and CCL5				X			X								X
Insulin/Glucose (HOMA-IR)				X											X
HbA1C				X						X					X
Plasma Renin/Aldosterone				X											X
Medication Log		X			X		X	X	X	X	X	X	X		X
Pill counts			X				X		X						X
Dietary survey/instructions		X													X
Urine sample (Albumin/Creat)	X	X	X				X		X						X
Urine Na/K/Creat			X												
Interim Event log			X		X		X	X	X	X	X	X	X		X
Questionnaire & Instructions		X													

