## **DISCONTINUATION OF SUBJECTS**

### **Early Discontinuation of Study Drug**

A subject may be discontinued from study treatment at any time if the subject, the investigator, or the Sponsor feels that it is not in the subject's best interest to continue. The following is a list of possible reasons for study treatment discontinuation:

Subject withdrawal of consent (or assent)

Subject is not compliant with study procedures

Adverse event that in the opinion of the investigator would be in the best interest of the subject to discontinue study treatment

Protocol violation requiring discontinuation of study treatment

Lost to follow-up

Sponsor request for early termination of study

Positive pregnancy test (females)

If a subject is withdrawn from treatment due to an adverse event, the subject will be followed and treated by the Investigator until the abnormal parameter or symptom has resolved or stabilized.

All subjects who discontinue study treatment should come in for an early discontinuation visit as soon as possible and then should be encouraged to complete all remaining scheduled visits and procedures.

All subjects are free to withdraw from participation at any time, for any reason, specified or unspecified, and without prejudice.

Reasonable attempts will be made by the investigator to provide a reason for subject withdrawals. The reason for the subject's withdrawal from the study will be specified in the subject's source documents.

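### The only required pregnancy test is at screening, so a woman who may become pregnant can start spironolactone at Visit 2 on a negative result about 2 to 4 weeks old

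*Combined protocol and SAP*

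**What the plan says.** The Reproductive Risks section of the combined protocol and SAP recognises that spironolactone may harm a fetus. It sets one test: "A pregnancy test will be required at screening for all woman who may become pregnant". It then makes the result binding: "A negative test is required for the individual to enroll in the study". No repeat is mentioned.

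Active drug does not start at screening. Under Method of Assigning Subjects to Treatment Groups, "All study participants will undergo a two week run-in period with placebo". Under Main Study Phase, patients are then "randomized 1:1 to Placebo or Spironolactone 12.5 mg on Week 0 (Visit 2"). The only eligibility item that the plan expressly rechecks after the run-in is blood pressure.

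The Exclusion Criteria list "Pregnant women and nursing mothers" without naming a visit. The Main Study Phase and Recruitment Strategy sections require all criteria to be met before randomisation. The Inclusion Criteria admit women of childbearing potential under a condition: "females must be either post-menopausal for one year, surgically sterile, or using effective contraception". Oral contraceptives are not allowed.

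Table 4, the main-phase schedule, has no pregnancy-test row at any visit. Its screening row reads "Screening Labs (BMP, Lipid panel, HbA1C, Urine sample Alb/Creat"), and its safety labs are a BMP only.

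**The concern.** An entry test for a drug with a fetal hazard should describe the woman's status when exposure begins. Here it describes her status at screening, before the run-in. The plan chose a negative test as its safeguard, so it did not regard contraception alone as enough. The timing then leaves the remaining screening time and the run-in uncovered.

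The other protections do not close this gap. Reporting a pregnancy and stopping the pills, and the listing of a positive test as a reason to discontinue, both act only once a pregnancy is recognised, and no on-study test is scheduled that would bring that about. Recognition may also be delayed on treatment, because Other Side Effects lists amenorrhea and irregular menses as drug effects, so a missed period can be put down to the drug.

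What is at stake is avoidable fetal exposure in a small number of women.

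**Working it through.** The plan states no figure for this interval, so there is none to reproduce. The check is calendar arithmetic on the schedule plus a reading of every section that bears on pregnancy.

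**Inputs**
- Screening occupies W1 and W2 (Table 4).
- The run-in is two weeks and begins at W3 (Table 4; Method of Assigning Subjects to Treatment Groups).
- Visit 2 is at W4 in Table 4 as extracted. It is at W5 if a full two-week run-in starts at W3 (3 + 2 = 5). The table's columns may be broken, so both readings are carried.
- Weekly visits have a window of ±2 days (Study Procedures and Guidelines).

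**Age of the negative result at first dose** = week of Visit 2 − week of the test

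| Test | Visit 2 | Gap | Gap with ±2 days at both visits |
|---|---|---|---|
| W2 | W4 | 2 weeks | 14 ± 4 = 10 to 18 days |
| W1 | W4 | 3 weeks | 21 ± 4 = 17 to 25 days |
| W2 | W5 | 3 weeks | 21 ± 4 = 17 to 25 days |
| W1 | W5 | 4 weeks | 28 ± 4 = 24 to 32 days |

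The nominal range is therefore 2 to 4 weeks, or 10 to 32 days with the visit windows. The final visit week does not settle where Visit 2 falls. W53 − 48 = W5 only if the 48 treatment weeks include escalation, whereas Method of Assigning Subjects to Treatment Groups puts the 4-week escalation before them.

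**What a Visit 2 test would change.** Let L be the time after conception during which a test cannot yet detect pregnancy; the documents give no value. With the test at screening, the undetected window before first dose is gap + L. With a test at Visit 2 it is L. The change removes the whole gap of 2 to 4 weeks and leaves L.

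**Two conditional extensions, neither needed for the finding**
- The Study Population section accepts labs drawn within 3 months of screening and does not say whether the pregnancy test is included. The natural reading is that the specific rule in Reproductive Risks governs. If the allowance did apply, taking 3 months as about 13 weeks before the W1 visit, the result would be 13 + 3 = 16 to 13 + 4 = 17 weeks old.
- Under the COVID-19 plan (Active Participants and Follow up Visits), patients in run-in have Visit 2 postponed. No maximum is stated and the follow-up labs are not specified. The length of the hold adds directly to the gap.

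**Is a later test required elsewhere?** The exclusion and the rule that all criteria be met before randomisation name no test. The discontinuation list gives no test date. Table 4 has no row, but that alone proves little, because the table also omits the screening test that Reproductive Risks requires. The conclusion rests on no section of the text requiring a second test.

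**The case against.** The strongest reply is that pregnancy is excluded right up to randomisation. The exclusion carries no visit qualifier, unlike the blood pressure, GFR and potassium items, so a site must judge pregnancy status at Visit 2. Contraception is mandatory throughout, and nothing in the plan is contradicted. On this view a second test is a preference. The duty to exclude is real, but without a test it reaches only a known pregnancy.

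Second, the plan relies on contraception and self-report for about 52 weeks (4 of escalation and 48 of treatment), so 2 to 4 more weeks of the same reliance adds little. It is true that the remedy covers a small part of the total time at risk. On-treatment testing is a separate question. The point here is narrower: the plan set an entry test, and its timing does not match entry to exposure.

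Third, a Visit 2 test would also miss a very recent conception. That is correct; it removes the gap and leaves the detection lag.

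Fourth, the 4-week end depends on placing Visit 2 at W5, whereas Table 4 as extracted puts it at W4. This stands as a caution about the upper end. At W4 the gap is still 2 to 3 weeks, so the conclusion does not change.

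Fifth, few women are affected, and the 16 to 17 week figure rests on a reading that is not the natural one. Both are accepted. The first is why the point is minor, and the second is why that figure is only conditional.

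**Conclusion.** The concern holds, as a minor safety point. A site that follows the plan exactly can give the first randomised dose of spironolactone to a woman with an unrecognised pregnancy, on a negative test about 2 to 4 weeks old. The range assumes that the test is done in W1 or W2 and that Visit 2 falls at W4 or W5. The gap is longer, without a stated limit, for anyone whose Visit 2 was postponed under the COVID-19 plan.

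The number of women exposed to this gap is not given and is probably small: entry is above age 45, or above 40 with a prior atherosclerotic event, and post-menopausal or sterile women are outside the test requirement. Endpoints, power and alpha are unaffected. The finding concerns the main study phase; in the open-label vanguard phase the schedule runs from screening at W1 to treatment at W2, a gap of about one week.

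**What to change.** In Reproductive Risks, in Method of Assigning Subjects to Treatment Groups and as a row in Table 4, require a negative urine or serum pregnancy test at Visit 2, before the first randomised dose, in every woman who may become pregnant. Keep the screening test. Apply the same rule to participants whose Visit 2 was postponed under the COVID-19 plan. In Study Population, state that the 3-month allowance for eligibility labs does not extend to the pregnancy test.

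The cost is one inexpensive test at an existing visit in a small subset. Clinical Assessments places the Na, K and creatinine collection used to estimate 24-hour urine at Visit 2, although Table 4 as extracted appears to put it at W3. If the urine timing differs, a serum test serves equally well, because Table 4 as extracted shows blood drawn at Visit 2. No extra visit or invasive procedure is needed.
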